### Visbiome Extra Strength Quality Assurance

Visbiome Extra Strength is classified by the Food and Drug Administration (FDA) as a "Medical Food," which is different than prescription drugs. Unlike prescription drugs, medical foods do not have to undergo premarket review and approval, nor can they make any health benefit claims. Medical foods must comply with all FDA requirements for foods, including, food Good Manufacturing Practices (GMPs) and other applicable regulations. (See

http://www.fda.gov/Food/GuidanceRegulation/GuidanceDocumentsRegulatoryInformation/MedicalFoods/)

Medical foods must be manufactured under the FDA's compliance program for medical foods. This is a manufacturing inspection program with the main objective of assuring the safety and integrity of the medical food products.

(http://www.fda.gov/downloads/Food/GuidanceComplianceRegulatoryInformation/ComplianceEnforcement/ucm073339.pdf)

The FDA does not require a written or oral prescription for medical foods, but does

require that a medical food be consumed or administered enterally under the supervision of a physician.

The PSWP contains a GMP statement document from the Visbiome Extra Strength manufacturer, DuPont, and a Product Description document from DuPont /Danisco. The Product Description document includes the composition, storage, microbiological testing specifications, and other descriptive information.

## Animal Studies of Visbiome

In animal models of colorectal cancer, dextran sulfate sodium (DSS)-induced colitis, and mice at risk for nonalcoholic steatohepatitis (NASH) and atherosclerosis, Visbiome has consistently demonstrated benefit in outcomes that are mediated through anti-inflammatory properties. In a rat model of DSS-induced colitis, rats treated with Visbiome prior to administration of DSS were protected from the development of colitis with marked reduction in disease activity index, as well as decreased neutrophil infiltration and myeloperoxidase (MPO) levels in colonic tissue (controls 8.6 + 0.8 mU/mg; DSS 21.9 + 1.2 mU/mg; DSS with Visbiome 12.2 + 0.9 mU/mg, p<0.05) [53]. With DSS administered alone, colonic protein expression was shifted to a pro-inflammatory milieu (increased inducible nitric oxide synthase (iNOS), COX-2, TNF-α, and IL-6 levels but decreased IL-10 levels). With co-administration of Visbiome and DSS, the colonic expression of these proteins was similar to levels seen in the control animals. Systemic markers of inflammation demonstrated similar results:

Group	TNF-α	IL-6	IL-10
Control	22.2 (2.3)	8.3 (1.3)	280.4 (2.5)
DSS	33.3 (2.0)*	44.1 (2.5)*	101.8 (2.3)*
DSS + Visbiome	24.9 (2.2)	14.5 (1.4)ŧ	240.8 (1.9)#

Data presented as mean (SE of each group). \* denotes p< 0.05 compared to control group. 
† denotes p<0.05 compared to DSS group.

Given that IL-6, TNF-α, and IL-10 are produced by macrophages and lymphocytes, these data indicate that Visbiome likely has important immunomodulatory effects on cells from both the innate and adaptive immune systems. Furthermore, reductions in iNOS and COX-2 expression indicate that Visbiome mediates its effect through antioxidant effects as well

These data were supported by another study in which a mouse model of colitis-associated colorectal cancer was used to assess the impact of Visbiome [54]. This colitis model was similar to that in the above study with the addition of chemically induced cancer or by infection with *Helicobacter typhlonius*. As above, Visbiome reduced disease activity scores, as well as decreased development of adenomas and adenocarcinomas. Mice receiving Visbiome actually demonstrated increased TNFα expression, which the authors suggested was related to antitumor and enhanced epithelial healing. Visbiometreated mice demonstrated increased expression of CD36 and PPARγ while upregulating angiotensin mRNA levels. PPARγ has been demonstrated to improve insulin sensitivity as well as block iNOS-related inflammation. Angiotensin expression likely limits the process of angiogenesis, which is a key component to early cancer development. Finally, mesenteric lymph nodes demonstrated greater IL-17 expressing CD4+ cells, Treg cells (CD4+FoxP3+ and CD4+CD44+CD62L+), and CD4+ memory

cells, cell populations that are depleted with HIV infection. This polarization of the lymphocyte population toward IL17 and T regulatory cells likely indicates a shift to an anti-inflammatory composition of the adaptive immune system. In summary, the data highlight the potent anti-inflammatory and immunomodulatory properties of Visbiome.

Another study utilizing the mouse DSS-induced colitis model went one step further to look at the impact of Visbiome on atherosclerosis, [55]. This study was based on the premise that atherosclerosis is an inflammatory process and persons with persistent inflammation (including HIV-infection, IBD, NASH, autoimmune and collagen vascular disorders) are at increased risk for more rapid progression of atherosclerotic lesions. Increased gut permeability in the setting of colitis contributes to increased systemic inflammation and thus, accelerates the process of atherosclerosis. The authors hypothesized that by repairing the gut mucosa and reducing gut permeability. Visbiome would reduce systemic inflammation and slow the atherosclerosis progression. In the animal model Visbiome restored gut permeability to that seen in DSS-naïve mice as evidenced by assessing plasma DXA-4000-FITC levels after an oral DSS challenge, by histopathological assessment with decreased inflammatory cell infiltration, and finally, by reducing the expression of inflammatory biomarkers (TNFα and RANTES). With improvements in gut permeability, there was less systemic inflammation as measured by levels of TNFα, RANTES, intracellular adhesion molecule-1 (ICAM-1), and macrophage inflammatory protein 1 alpha (MIP-1α) in the liver, and levels of RANTES, ICAM-1, and MIP-1α expressed in the aorta. Additionally, after Visbiome administration, circulating Tcells expressed lower IFNy and higher IL-10 thus, attenuating the DSS-induced shift to a Th1 inflammatory profile. Finally, as noted in the previous trial, intestinal expression of certain nuclear receptors was increased with Visbiome administration, including PPARy, FXR, and VDR. These receptors are involved in improving insulin sensitivity and modulating immune responses. In addition, in a recent study in SIV-macaques, Visbiome decreased the plasma KT ratio, a marker of IDO activity, an enzyme that has been demonstrated to be linked to HIV-associated pathogenesis in the GALT [56-59].

#### Human Studies of Visbiome

In summary, these animal colitis models highlight that Visbiome improves outcomes mediated through both improved gut permeability and anti-inflammatory and immunomodulatory effects. Human studies in IBD and cirrhosis have provided similar readouts. A recent study assessed changes in microbiome in 10 persons with irritable bowel syndrome (IBS) who were given Visbiome for 4 weeks [60]. At baseline, the IBS participants had lower diversity than control subjects with increased *Bacteroides*, *Eggerthella*, and *Cloasibacillus sp* and decreased *Flavobacterium*, *Actinomyces*, *Veillonella*, *Dorea*, and *Roseburia sp* (p<.05 for all). Clinically, 6/10 IBS participants had reduced symptoms at the time of evaluation (4 weeks). With probiotic therapy, the subjects had increased diversity with significant increases in *Bifidobacteria*, *Lactobacillus*, and *Streptococcus sp* in the mucosal biopsy specimen. Thus, Visbiome clearly alters the microbiome to one that is more similar to the healthy controls after only 4 weeks of administration.

From an ongoing randomized controlled trial (RCT) randomizing persons with UC to receive either Visbiome or placebo for 8 weeks, Ng et al reported on a subset of participants who underwent additional testing to evaluate the mechanism of Visbiome

action [61]. In this small cohort, 10/14 Visbiome recipients (71%) versus 4/14 placebo recipients (29%) had a clinical response to therapy (p =0.068). Notably, Visbiome significantly downregulated toll-like receptor 2 (TLR-2) expression with similar trends in TLR-4, CD40, and CD86 expression. Furthermore, IL-10 production was increased while IL-12 was decreased with administration of Visbiome. These data indicate that Visbiome impacts UC disease severity by modulating immune responses.

Another RCT assessed the potential for Visbiome as an adjuvant to beta blocker therapy to improve portal hypertension in cirrhotic participants with severe esophageal varices [62]. The authors hypothesized that improving gut permeability would reduce bacterial translocation and hepatic inflammation and thus, reduce portal pressures. After 2 months of Visbiome administration, portal pressures and large varices were reduced in 15/25 (60%) of Visbiome recipients versus only 7/27 (27%) of propranolol with placebo (p=0.025). TNF-α concentrations significantly declined in peripheral blood and hepatic venous blood with Visbiome when compared to placebo. No difference was detected with regards to IL-6 or serum nitrate levels. Nevertheless, there was clinical benefit with a signal suggesting that decreased inflammation was a potential mechanism of action.

Studies have also evaluated the effect of Visbiome in the setting of obesity, an epidemic comorbidity in the US and one that is becoming more common among HIV-infected patients. In an RCT of 60 overweight participants, persons with lipid abnormalities, insulin resistance, and high-sensitivity c-reactive protein (hsCRP) >3 mg/L had lower diversity at baseline, specifically with decreased *Lactobacilli*, *Bifidobacteria*, and *Streptococcus* yet higher *E. coli* and *Bacteroides sp.* [63]. These data indicate that dysbiosis is associated with a poorer overall health status. After Visbiome administration, microbial diversity was significantly increased compared to persons who received placebo, including total aerobes, total anaerobes, *Lactobacillus*, *Bifidobacteria*, and *Streptococcus sp.* After administration of Visbiome, insulin sensitivity improved and hsCRP declined (p<0.05 within group and between groups for both). Furthermore, there were modest declines in IL-1β, TNFα, and IL-6 with Visbiome administration.

A similar trial in obese children has recently been reported [64] in which 44 obese children with NASH were randomized to Visbiome or placebo. After 4 months of therapy, both groups experienced improvements in insulin resistance but the Visbiome group had improvements in glucagon-like peptide-1 (GLP-1) and glucagon-like peptide-1 receptor agonists (aGLP-1) levels. Furthermore, liver inflammation and steatosis decreased and body mass index (BMI) declined significantly with Visbiome administration. The authors concluded that the restoration of a normal gut flora led to increased short-chain fatty acid (SCFA) production, which resulted in the production of anorexogenic gut hormones (GLP-1 and aGLP-1) and improved insulin sensitivity with BMI reduction.

A small study of critically ill participants evaluated whether Visbiome would improve inflammation and lipid parameters [65]. In this study, 40 participants were randomized to 7 days of Visbiome or placebo. Despite the short course of therapy and high severity of illness scores at baseline, the Visbiome recipients experienced significant declines in hsCRP and TG levels and increases in HDL-c levels (p<0.05 for all). While no data were collected regarding microbiome or more sophisticated analyses of immunity, the data support the hypothesis that Visbiome will reduce inflammatory parameters.

## Visbiome in SIV-infected Macagues

The promising effects of probiotics on gut dysbiosis and inflammation were also evaluated in SIV-infected macagues [66]. In this study, eleven macagues treated with ART were studied; four received ART alone and seven also received Visbiome with inulin for 5 months. Interestingly, there were no microbiome changes seen with SIV infection and only modest changes seen with administration of Visbiome. Peripheral CD4+ counts increased similarly in both groups but there were striking differences in certain cell populations and in gene expression in the cells isolated from the GI mucosa at necropsy. A significantly greater number of antigen presenting cells (APC), and specifically HLA-DR+ APCs, were measured from the Visbiome animals; these cells had increased gene expression for HLA-G, HLA-DB3, HLA-H, CD14, and CD68. As a consequence, IL-23 levels were significantly higher among the macaques receiving Visbiome, Furthermore, colonic CD4+ T-cells were reconstituted to near normal levels with Visbiome administration despite confirmed massive depletion with SIV infection. Notably, these CD4+ T-cells were more often multifunctional (defined as producing at least two of the following cytokines: IL-17, TNF-α, or IL-2). Additionally, T-cell activation was reduced in the colonic mucosa, as measured by Ki67 expression. While none of the systemic markers of immune activation were significantly decreased, this likely reflects that the sample size of 11 individuals prohibits the ability to assess differences in these highly variable measures. In summary, this research demonstrates that Visbiome facilitated a reconstitution of colonic CD4+ cells, and enhanced gastrointestinal immune function in this highly relevant SIV model.

### Probiotics in HIV-infected Persons

The therapeutic effects of probiotic products have also been studied in the setting of HIV infection [66-81]. Results from these studies have been mixed for various reasons. One approach that consistently fails to demonstrate benefit is the use of probiotics in the setting of uncontrolled HIV infection [76, 77, 82]. Without control of viremia, the impact of probiotics is negligible at best. However, when given in the setting of virologically suppressive ART, probiotics have demonstrated significant benefit. In an RCT of 17 virologically suppressed participants, Yang et al showed that Bacillus coagulans GBI-306086 capsule probiotic demonstrated no benefit on CD4+ count but significantly improved CD4 percentages and reduced sCD163 levels. An alternative probiotic study of Lactobacillus rhamnosus in a cohort of virologically suppressed individuals demonstrated a significant increase in total CD4+ T-cells [73]. In recently presented data on Visbiome probiotic supplementation in a cohort of 20 HIV-infected, ART-suppressed individuals and 11 seronegative controls [59], CD4+ and CD8+ T-cell activation, characterized by CD38+/HLA-DR+ co-expression, was decreased after 3 months of probiotic supplementation to levels seen in the seronegative controls. sCD14 and Ddimer levels were relatively stable over the brief intervention, but lipopolysaccharidebinding protein (LBP) was reduced to levels of the control participants, suggesting that bacterial translocation was reduced with the probiotic. While this study was small in size, the data are consistent with the results previously reported in SIV-infected macaques. Therefore, further investigations in appropriately powered human trials are needed.

These results suggest that Visbiome is a promising adjunctive probiotic therapeutic approach with ART to improve gastrointestinal damage and inflammation in HIV-infected

patients. We hypothesize that administration of Visbiome will alter the gut microbiome, positively impact gut mucosal integrity, decrease systemic markers of inflammation and immune activation, and improve other metabolic parameters.

### 2.2 Rationale

We propose to conduct a phase II, randomized two-arm study with Visbiome Extra Strength and matching placebo in HIV-infected participants on stable ART with CD4+ count >200 c/mm³ and plasma HIV-1 RNA <50 copies/mL to better understand the effects of this probiotic product on reduction in bacterial translocation and systemic immune activation.

The selection of the CD4+ cell count cutoff level was guided primarily by safety issues [83]. According to a 2002 report released by the World Health Organization (WHO) and the Food and Agriculture Organization (FAO) of the United Nations (http://www.fda.gov/ohrms/dockets/dockets/95s0316/95s-0316-rpt0282-tab-03-ref-19joint-faowho-vol219.pdf), there are four potential safety concerns for probiotics: 1) systemic infection, 2) metabolic complications, 3) excessive immune activation, and 4) gene transfer especially of antimicrobial resistance. Of these four, only systemic infection has been reported in the literature, including several cases of bacteremia, sepsis, endocarditis, and abscess from organisms present in probiotic preparations. While reports of infections related to probiotic bacteria have been published, these cases have primarily occurred in persons with short gut syndrome, recent gastrointestinal procedure, or severe immunosuppression (recent surgery; bone marrow, stem cell, or solid organ transplantation; uncontrolled diabetes; cancer; and advanced AIDS [ie, CD4+ count <200 cells/mm^3]. Population-based studies in Sweden and Finland are reassuring as they showed no increase in the rate of bacteremia of common probiotic bacteria such as Lactobacillus sp., despite dramatic increases in the use of probiotics [84, 85]. In addition to the potential safety risk for persons with low CD4+ cell counts, potential participants with a CD4+ ≤200 cells/mm³ would require prophylactic antibiotics for opportunistic infections (OIs); thus, these participants would be excluded since antibiotics will alter the intestinal microbiome. Therefore, to maximize participant safety and limit potential confounding from OI prophylactic antibiotics, this study will only enroll HIV-infected participants with CD4+ cell count >200 cells/mm^3.

The rationale for only enrolling participants with a plasma HIV-1 RNA <50 copies/mL is based on knowledge that probiotic products consistently fail to demonstrate benefit in the setting of uncontrolled HIV infection [77, 80, 82]. Without controlled viremia, the impact of probiotics is negligible at best. However, when given in the setting of virologically suppressive ART, probiotics have demonstrated benefit.

The rationale for excluding persons with significant weight change (defined as 25 pounds) in the past 24 weeks is related to the fact that previous research has demonstrated a strong association between the gut microbiome and BMI [86-88]. If participants have had a recent change in their weight, the gut microbiome may not be stable at the time of entry.

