# 1.6 Exploratory Objectives

- 1.6.1 To assess changes in a marker of insulin sensitivity (HOMA-IR) after administration of Visbiome Extra Strength.
- 1.6.2 To assess changes in fasting lipid parameters (LDL, high-density lipoprotein [HDL], non-HDL cholesterol, and triglycerides) after administration of Visbiome Extra Strength.
- 1.6.3 To explore the correlations between the gut microbiome and soluble and cellular markers performed in the study.
- 1.6.4 To explore the correlations between the microbial translocation markers and other soluble and cellular markers performed in the study.
- 1.6.5 To assess durability of the probiotic effect on inflammatory and microbial translocation markers 12 weeks after discontinuation of Visbiome Extra Strength therapy.
- 1.6.6 To assess the differences in composition of the baseline microbiome based on ART.
- 1.6.7 To assess changes in chronic gastrointestinal symptom score after administration of Visbiome Extra Strength.
- 1.6.8 To assess the relationship between reported dietary intake and composition of the microbiome.

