#### NOTES:

- Diarrhea is defined as three or more stools per day that are liquid/loose/watery and will take the shape of a container. If the duration of loose stools meeting this criterion definition is greater than 30 days, this is chronic diarrhea and is not exclusionary.
- 2. Acute diarrhea is defined as 3-14 day duration.
- 3. Persistent diarrhea is defined as 15-30 day duration.
- 4.2.17 Weight loss or gain of more than 25 pounds in the 24 weeks prior to study entry.

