# 6.3.6 Height

Height will be recorded at the screening visit only.

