# 9.6 Analyses

All statistical tests will be two-sided with a nominal alpha level of 0.05. Because this is a phase II study and all potential biologic activities of the intervention are of interest, analyses will be as-treated, and limited to participants who 1) have baseline and week 26 sCD14 measurements, 2) remain on study product through week 26 (participants with more than 50% on average of missed study product may be excluded), 3) have not used prohibited medications, 4) do not have a confirmed virologic failure (as defined per section 6.2.3 at or prior to week 26, and 5) do not experience inflammatory conditions, receive vaccines, or have concurrent illness (as defined per section 6.2.3).

NOTE: Participants experiencing inflammatory conditions at the time of a visit are instructed to wait 7 days before measurements are obtained. Measurements obtained while inflammatory conditions are present will not be included in the analysis. A supplemental intent-to-treat analysis will also be performed and will include all randomized participants. No adjustment for multiple testing will be performed. A summary of the number of participants experiencing study product-related AEs and the types of AEs will be reported, as will the proportion of participants who discontinue study product after entry.

To reduce intra-participant variability, two blood draws will be performed at baseline (entry and week 2) and week 26 (week 25 and week 26) and the measurements will be the average of two for sCD14. If repeat measurements are not available at either of these time points, a single measurement will be used rather than the average.

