#### 9.6.2 Secondary Analyses

Similar to the initial primary analysis regression model, changes in other outcome measures will be compared between the Visbiome Extra Strength and placebo arms by linear regression. For these models each participant will have a single outcome measure of change from baseline to week 26. The only predictor variable will be study arm.

The weeks 26 and 38 levels of the primary, secondary, and exploratory outcome measures will be compared with baseline levels through linear regression.

Spearman correlations will be used to evaluate correlations between changes in select outcome measures. In addition, longitudinal changes in these measures will be examined using graphical approaches, descriptive statistics, and possibly repeated measures modeling.

Safety will be evaluated by summarizing the nature and rate of AEs within each study arm for all participants initiating study product. Comparisons of overall and AE-specific grades between study arms will be evaluated with an exact test for ordered categorical data (Wilcoxon rank-sum test of the maximum grade for each participant). Study product tolerability will be evaluated by summarizing study product modifications and discontinuations by study arm.

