4.4 Statistical Summaries and Testing

All statistical tests will be two-sided with a nominal alpha level of 0.05 and no adjustment for multiple testing.

Specimens collected 1 day after the last dose of study treatment will be considered "on treatment".

Specimens collected within 6 days of an influenza vaccination will not be used for analysis unless the vaccination and specimen collection occurred on the same date and the site has documented that the vaccination was given after specimen collection.

Outcome measures will be transformed for analyses and summaries on the log₁₀ scale, as appropriate, if determined to not be approximately normally distributed.

Because the stratification is to ensure balance between the treatment arms within A5352s and is not felt to affect A5350 outcomes, the stratification will not be taken into account in analyses.

Safety analyses will summarize the highest grade AE by participant using the mITT population and will compare treatment arms using the Wilcoxon rank-sum test. All AEs and AEs related to study treatment will be analyzed.

For all continuous outcome measures, tabular and graphical data summaries will be provided for both cross-sectional values across study weeks and change from baseline to post-baseline study weeks and will use the PP population. Mean changes in outcome measures will be compared between arms with either a two-sample t-test with equal variances or an adjusted linear regression model, as appropriate. The mean difference and 95% confidence interval (CI) will be provided along with the associated p-value.

For the primary analysis, two supplemental linear regression analyses will be performed. The first will additionally adjust for baseline sCD14 values (continuous) while the second will assess differential Visbiome Extra Strength

effects by baseline sCD14 tertile by additionally adjusting for the sCD14 tertile main effect and the study arm by sCD14 tertile interaction.

Correlations will be assessed with scatter plots as well as the Spearman correlation coefficient and associated p-value using the PP population.

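### Baseline-only microbiome analyses (by ART regimen and by diet) should use every randomised participant with a week 2 stool sample, not the as-treated/per-protocol set

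*Protocol*

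**What the plan says.** Two exploratory objectives in Protocol 1.6 can be answered wholly or partly before treatment: "To assess the differences in composition of the baseline microbiome based on ART" (1.6.6) and "To assess the relationship between reported dietary intake and composition of the microbiome" (1.6.8). In the Schedule of Events the first stool sample and a dietary assessment fall at week 2, before the first dose.

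On who is analysed, Protocol 9.6 states that "analyses will be as-treated, and limited to participants who" meet five conditions. They must have baseline and week 26 sCD14, remain on product through week 26, not have used prohibited medications, have no confirmed virologic failure by week 26, and have no inflammatory condition, vaccine or concurrent illness. SAP 4.1 carries the same conditions into its PP definition, with week 25/26 sCD14 and eligibility added. SAP 4.4 places continuous outcome summaries in that population, and for associations it says: "Correlations will be assessed with scatter plots as well as the Spearman correlation coefficient and associated p-value using the PP population".

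Protocol 9.6 also promises a supplemental intent-to-treat (ITT) analysis of all randomised participants. SAP 4.1 defines ITT, but SAP 4.4 assigns it to no analysis; safety uses mITT and the rest uses PP. SAP 3.2 and 3.3 mark the fecal microbiome outcomes, including diversity with diet, as not analysed at SDAC.

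On BMI, Protocol 2.2 says that "previous research has demonstrated a strong association between the gut microbiome and BMI". It uses this only to justify exclusion 4.2.17, "Weight loss or gain of more than 25 pounds in the 24 weeks prior to study entry". BMI level is not restricted. "Height will be recorded at the screening visit only", and weight is also taken at screening, so screening BMI can be derived. No analysis text names it.

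**The concern.** The PP conditions suit a question about biological activity of the product at week 26. They have no bearing on whether the microbiome differed between ART regimens, or varied with diet, before anyone took a sachet. A participant who stops product at week 10, has a flu-like illness at week 20 or lacks an end-of-treatment sCD14 result has still given a valid week 2 stool sample and diet record.

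Two things are at stake. The first is precision, in objectives where a 90-person trial has little to spare. The second is selection: the baseline sample would be filtered by later adherence, illness and virologic control. Virologic failure is tied directly to the ART regimen, the grouping variable in 1.6.6. The documents give no basis for the direction or size of any resulting bias, but it can be avoided at little cost.

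A secondary matter is that 1.6.6 and 1.6.8 are non-randomised comparisons, and the protocol itself names BMI as strongly related to the microbiome. An unadjusted association could therefore reflect BMI.

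**Working it through.** **1. The plan's own figures.** Protocol 9.4 inflates 36 per arm to 45 for 20% missing data: 36 / (1 − 0.20) = 45, which reproduces. The 95% half-width at 36 vs 36 is t(0.975, 70 df) × √(2/36) = 0.470 SD, matching the stated 0.47. Power at 0.77, 0.67 and 0.59 SD is 89.6%, 80.1% and 69.5% by the noncentral t, matching 90/80/70%.

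**2. Each PP condition against a week 2 question.**

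| Condition | When determined | Needed for a baseline comparison? |
|---|---|---|
| Baseline and week 26 (SAP: 25/26) sCD14 | end of treatment | No |
| On product through week 26 | weeks 2–26 | No |
| No prohibited medication | while on product (5.4.2) | No |
| No confirmed virologic failure | up to week 26 | No |
| No inflammatory condition, vaccine or illness | during follow-up | Only if present at the week 2 draw |

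For the last row, Protocol 9.6 already says that measurements taken while an inflammatory condition is present are not used. That handles the sample without removing people who became ill later.

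**3. Precision.** Interval width is proportional to 1/√n, so the ratio of width with all 90 to width with n participants is √(n/90). The documents do not give the size of the PP set; 72 comes from the 20% allowance, and 10% and 30% losses bracket it.

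| PP size assumed | √(n/90) | Intervals narrower by |
|---|---|---|
| 81 (10% lost) | 0.949 | 5% |
| 72 (20% lost) | 0.894 | 11% |
| 63 (30% lost) | 0.837 | 16% |

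The 20% was set for laboratory problems and loss to follow-up, so conditions 2 to 5 could push the PP set below 72. Conversely, not all 90 will have a usable week 2 stool sample.

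**4. BMI in the non-randomised objectives (all correlations assumed; n = 72, nominal 5% test, 20,000 simulated trials each).** Diet and diversity have no direct link, and each correlates r with BMI.

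| r | BMI a common cause: plain / partial Spearman | BMI a common effect: plain / partial Spearman |
|---|---|---|
| 0.3 | 11% / 5% | 5% / 11% |
| 0.4 | 25% / 5% | 5% / 29% |
| 0.5 | 52% / 5% | 5% / 73% |

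Adjustment helps or harms according to causal direction, and the trial's data cannot settle that.

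**5. BMI in the arm comparison of diversity.** The outcome at week 26 is a change score. With equal variances, the correlation of BMI with change is (r26 − r0) / √(2(1 − w)), where w is the within-person correlation. If r is stable, this is 0. If r drifts from 0.3 to 0.2 with w = 0.6, it is −0.1/√0.8 = −0.112, so R² = 0.0125. At 0.67 SD, power is 80.1% unadjusted, 80.4% at R² = 0.01 and 80.8% at R² = 0.02. Omitting BMI therefore costs less than one point.

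**The case against.** **ITT is already planned.** Protocol 9.6 does promise a supplemental ITT analysis. That stands in part: the population exists and is defined. But it is supplemental to an as-treated analysis, and the SAP gives it no task, so nothing makes it the main set for a baseline question.

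**The microbiome work is outside SDAC, so SAP 4.4 may not bind it.** This is fair, since another plan may exist. However, Protocol 9.6 makes no exception for any analysis group, and no other population is stated for these objectives. That is a reason to write the rule so that it applies whoever does the work.

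**A stronger reading on BMI.** A reader might infer from the BMI statement in 2.2 that BMI must be a covariate in every microbiome model, and that the arm comparison loses precision without it. The documents do not support this. The sentence "The only predictor variable will be study arm" concerns change to week 26, where a stable BMI effect cancels. SAP 4.4 allows an adjusted regression where appropriate, without naming covariates for it. No between-arm model of the week 38 diversity level is specified; if one were run, baseline diversity would be the more useful covariate and would absorb a stable BMI effect. Randomisation protects the arm comparison from bias.

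Nor does BMI adjustment give the correct answer for 1.6.6 and 1.6.8. Protocol 2.1 reports a trial in obese children whose authors attributed lower BMI to restored gut flora, so BMI may be a consequence of the microbiome. It may also lie on the path from diet or ART to the microbiome, in which case adjustment removes part of the effect being sought. Test-rejection figures for ART classes at 36 vs 36 would not apply either: that is the evaluable number per randomised arm, and hypothesis 1.3.6 names three classes of unknown size.

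**Conclusion.** The analysis-set point holds. As written, the rule removes participants from baseline-only analyses for reasons that arise after baseline and are irrelevant to the question. The avoidable loss is about 11% in interval width if 72 of 90 remain, and 5% to 16% if 10% to 30% are lost. These figures assume that the PP set follows the missing-data allowance or that bracket, and that week 2 stool samples are nearly complete. Selection is possible but cannot be sized from the documents.

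On BMI, only a modest point survives: the ART and diet comparisons are non-randomised, so a BMI-adjusted companion result would inform readers. It should not replace the unadjusted result or be read as removing confounding. A claim that the arm comparison of diversity loses material precision should not be made.

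This is a minor point, confined to exploratory objectives.

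**What to change.** In Protocol 9.6 and SAP 4.4, state that analyses using only pre-treatment microbiome data (objective 1.6.6 and the baseline part of 1.6.8) include all randomised participants with a week 2 stool sample, whether run at SDAC or elsewhere. Keep the existing rule that a sample taken during an inflammatory condition is not used. Post-treatment parts of 1.6.8 can stay in the PP set.

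Optionally, for the same two objectives, report a result adjusted for screening BMI (continuous) beside the unadjusted one. Label it a sensitivity analysis and note that BMI could be a confounder, a mediator or a consequence.

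The cost is a sentence in each document, with no new visits or samples. If stool sequencing would otherwise have been limited to the PP set, about 90 − 72 = 18 more week 2 samples need assaying, though the promised ITT analysis would call for them anyway. The group analysing the microbiome would need the population definition and, for the option, screening height and weight.
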